#### **From Visit 10 to Visit 14: Mandatory stable OCS dosage**

OCS dosage must be stable unless medically justified by the investigator.

No increase in OCS is allowed after Visit 10 except for managing AEs or as prophylaxis for adrenal insufficiency.

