## 6.2.2 Allowed concomitant therapy

Allowed concomitant therapy include medications allowed under certain conditions.

Allowed medication	Conditions of use
CS burst	See Section 6.2.2.1.
NSAIDs	See Section 6.2.2.2.
Low-dose aspirin	Stable long-term use of low-dose aspirin (maximum of 325 mg/day) for cardiovascular disease is permitted.
Non-NSAIDs pain medications	Temporary use of pain medications (e.g., acetaminophen/paracetamol or other non-NSAID pain medication) may be used for pain management as required, based on Investigator judgment for up to 1 week at a time and should not be taken on the day of a scheduled visit until all assessments have been completed.
Topical therapy	Topical ocular therapy (e.g., chronic treatment for glaucoma, ocular inflammation, allergy), including dilating eye drops, mydriatics, parasympathetic antagonists (e.g., tropicamide) or sympathetic agonists (e.g., phenylephrine). Topical skin therapy, inhaled and nasal therapy, including topical use of CS.
Atropine	Permitted i.v. in the event of symptomatic bradycardia.
Vaccination	Only non-live vaccines.

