### 6.2.2.1 CS burst conditions of use

#### From Visit 2 to Visit 10

Participants who experienced increased SLE disease activity may receive *one* CS burst (after study visit assessments). Only one burst can be administered between Visit 2 and Visit 10, as follows:

- OCS dose increase up to a maximum daily dose of 40 mg/day prednisone or equivalent [see Appendix 12] up to a total of 14 days. This OCS increase must be fully administered and tapered to less than or equal to the Day 1 (Visit 2) dose by no later than Visit 10.

*or*
- Intramuscular methylprednisolone ( $\leq$  80 mg or equivalent) administered as a single dose.

*or*
- A maximum of 2 intra-articular / tendon sheath / bursal injections (for a total methylprednisolone  $\leq$  80 mg or equivalent) at the same visit.

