## **From Visit 10 to Visit 14**

No CS burst allowed.

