### **9.2 Description of statistical analyses**

All available data (regardless of whether collected during scheduled or unscheduled visits) for each participant will be used in all statistical analyses unless otherwise specified.

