### **9.2.4 Analysis of efficacy endpoints**

The following variables will be descriptively analyzed and summarized by month using the SS.

- The observed mSLEDAI-2K total score and change from baseline  
Please refer to Appendix 6 for the detailed information.
- Observed SRI-4 response.  
A participant will be assessed as a SRI-4 responder if they meet ALL the below criteria:
  1. Reduction from baseline of at least 4 points in the mSLEDAI-2K;  
and
  2. No new BILAG A organ domain score and no more than one new BILAG B organ domain score compared with baseline;  
and
  3. No increase of more than 0.3 points on the PGA Score since baseline;

If 1 of the 3 components is missing, the SRI-4 response will be missing for this assessment, unless 1 of the non-missing components is not met. In that case, the participant will be assigned a non-response status for SRI-4.

- Observed BICLA response.  
A participant will be assessed as a BICLA responder if they meet ALL the below criteria:
  - 1) Improvement from baseline in disease activity as measured by BILAG-2004. Improvement is defined as a reduction of all baseline BILAG-2004 A to B/C/D and baseline BILAG-2004 B to C/D and no BILAG-2004 worsening in other organ systems, where worsening is defined as  $\geq 1$  new BILAG-2004 A or  $\geq 2$  new BILAG-2004 B.

- 2) No worsening from baseline in mSLEDAI-2K score, where worsening is defined as an increase from baseline of > 0 points.
- 3) No worsening from baseline in the participant's lupus disease activity, where worsening is defined as an increase of 0.3 points or more on a 3-point PGA VAS score.
- 4) No discontinuation of study treatment.

If 1 of the 4 components is missing, the BICLA response will be missing for this assessment, unless 1 of the non-missing components is not met. In that case, the participant will be assigned a non-response status for BICLA.

- Response on CLASI from baseline to Month 12.  
Please refer to Appendix 10 for the detailed information.
- Change from baseline in tender and swollen joints.

The total tender joint count will be derived at each assessment, by summing the number of tender joints (= 1) as derived above. The total tender joint count values range from 0 to 28. If at least one joint was not assessed for tenderness or was not evaluable, the total tender joint count will be missing.

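### SRI-4 and BICLA in section 9.2.4 have no corticosteroid component, so a participant given a burst that section 6.2.2.1 bars can still be counted as a responder at later assessments (minor)

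*Combined protocol and SAP*

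**What the plan says.** **Responder definitions.** Section 9.2.4 summarises efficacy descriptively by month in the safety set. For SRI-4 it states: "A participant will be assessed as a SRI-4 responder if they meet ALL the below criteria". Three criteria follow: a fall of at least 4 points in mSLEDAI-2K, a BILAG criterion ("No new BILAG A organ domain score and no more than one new BILAG B organ domain score compared with baseline") and a limit on PGA worsening. BICLA has four: BILAG improvement, no mSLEDAI-2K worsening, no PGA worsening, and "No discontinuation of study treatment". Study treatment here means cenerimod. Section 9.2 adds that the available data "for each participant will be used in all statistical analyses unless otherwise specified".

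**Corticosteroid rules.** Section 6.2.2 lists the CS burst among allowed medications, with the condition "See Section 6.2.2.1". That section says: "Only one burst can be administered between Visit 2 and Visit 10, as follows". The options are an oral course of up to 14 days, a single intramuscular dose, or up to two local injections at one visit. For Visit 10 to Visit 14 it says: "No CS burst allowed". On oral CS (OCS), section 6.2.1.2.3 says: "No increase in OCS is allowed after Visit 10 except for managing AEs or as prophylaxis for adrenal insufficiency".

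**Stopping rule.** Section 6.2.3 lists therapies whose initiation forces permanent discontinuation of cenerimod, and section 5.8.1.9 points to that list. It names no corticosteroid.

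**The concern.** The protocol limits steroids partly so that efficacy can be interpreted. Section 6.2.1 warns that changing background medication after Day 1 can obscure the treatment effect, and section 4.3 gives interpretability as the reason for stopping the taper late in treatment. Yet the two composite endpoints do not react when the burst limit is breached. A second or late burst for SLE activity can suppress the disease, and a later assessment that compares scores with baseline can then record a response. With no control arm, that improvement would be credited to cenerimod and would push both response rates upward.

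The separate endpoint on OCS dosage does not close the gap. It does not feed into responder status, and because it covers oral CS only it would not show an intramuscular or joint injection.

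**Working it through.** The plan gives no figure to reproduce here: section 9.4 states about 15 participants without a derivation. The check has three parts.

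**1. Apply the rules as written.** Take a participant with mSLEDAI-2K change of −4, no new BILAG A or B, all baseline A and B grades improved, PGA change of −0.2, still on cenerimod.

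| Steroid history | SRI-4 | BICLA |
|---|---|---|
| No burst | responder | responder |
| Second burst before Visit 10 | responder | responder |
| Burst after Visit 10 | responder | responder |

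The burst enters neither rule.

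**2. Which assessments are exposed.** In Table 2, Visit 3 is Month 1, Visit 10 is Month 8 and Visit 14 is Month 12, giving 12 monthly post-baseline assessments (Visits 3 to 14).

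- Burst given just after the Visit 10 assessments: Visits 11 to 14 follow, 4 of 12.
- Second burst at Visit 4, an extreme case because it needs two bursts by Month 2: Visits 5 to 14 follow, 10 of 12.

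These are upper limits. Visits are nominally 30 days apart, BILAG looks back 4 weeks (28 days) and SLEDAI-2K looks back 10 days. A flare between visits will usually fall in the BILAG window of the next visit and may cause non-response there. Section 6.2.2.1 also places the burst after that visit's assessments, so activity present that day is scored before the steroid is given. What remains exposed is later: for a flare scored and treated at Visit 11, the recall windows at Visits 13 and 14 no longer reach back to it, and Visit 14 is the Month 12 endpoint.

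**3. Size.** Each affected participant who meets the score components adds at most 1/n to each rate.

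- n = 15: 1/15 = 6.7 points; 2/15 = 13.3; 3/15 = 20.0. The range of 0 to 3 affected is an assumption.
- n = 12 evaluable (assumption): 1/12 = 8.3 points.

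For scale, take exact (Clopper-Pearson) 95% limits: the lower is the 2.5% point of Beta(x, n−x+1) and the upper is the 97.5% point of Beta(x+1, n−x). With an illustrative count:

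- 7/15 = 46.7%, interval 21.3% to 73.4%.
- 6/15 = 40.0%, interval 16.3% to 67.7%.

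Reclassifying one participant moves the estimate by 6.7 points, against an interval 73.4 − 21.3 = 52.1 points wide.

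**The case against.** **It is a stated choice.** Section 9.2.4 labels both variables as observed responses, and section 3.2 wants endpoints that can be compared with other studies. As-observed reporting is defensible. This stands, and is why those rates should be kept beside any stricter version.

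**It needs a deviation.** Barred bursts are prohibited, and section 10.7 permits no waivers. This also stands and limits the weight of the point.

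**Flares are already captured.** A reader might infer that a rescued flare never counts. The documents do not support that, given the BILAG window and the timing of bursts after assessments. The SLE Flare Index is also scored at each treatment visit and includes prednisone increases, though it is not a section 9.2.4 endpoint. Only later assessments are exposed.

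**Discontinuation may follow anyway.** Section 6.2.2 allows medicines under conditions, so a burst outside them could be read as a forbidden immunosuppressant under section 6.2.3, which would fail BICLA. The text does not say this: the first bullet of 6.2.3 concerns agents not listed as allowed, and the CS burst is listed. SRI-4 has no discontinuation item, so it would be unaffected on either reading.

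**A late OCS increase might be permitted as AE management.** A reader might infer that recording a flare as an AE opens a permitted route to extra OCS after Visit 10. Section 8.1.1 does include medically relevant exacerbations, but its next bullet makes an exception for efficacy endpoints and their symptoms. That route is not established, and the point does not rely on it.

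**The permitted burst also confounds.** True, and the proposed rule leaves it alone. The rule enforces the plan's own limit and does not remove all steroid confounding.

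**The SAP may cover it.** Section 9 leaves derivation algorithms to the SAP. The supplied text contains no such rule, but one elsewhere cannot be excluded.

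**Conclusion.** The gap is real but minor. As section 9.2.4 is written, a barred CS burst for SLE activity does not prevent a participant who stays on cenerimod from counting as an SRI-4 and BICLA responder at later assessments.

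The effect is up to 6.7 points per affected participant with 15 evaluable. It depends on a deviation whose frequency the documents do not give, and on the participant meeting the score components afterwards.

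A reader might infer that the efficacy results would be materially biased or a conclusion put at risk. That does not follow. Efficacy is listed under the other objective, is preliminary and descriptive, and no test, sample size or decision rule depends on it; one such participant lies well within sampling imprecision. The change is optional and worth making because it is cheap and the bias it removes runs in one direction.

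**What to change.** In section 9.2.4 and the SAP, report SRI-4 and BICLA with this rule:

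> A participant who receives a CS burst (oral, intramuscular, i.v., or intra-articular, tendon sheath or bursal) with SLE activity as the recorded eCRF indication, beyond the single burst allowed in 6.2.2.1 or at any time after Visit 10, is a non-responder at all assessments after that burst starts. The one permitted burst, OCS returned to the pre-taper dose, and CS for non-SLE AEs or adrenal insufficiency do not count.

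Show the as-observed rates alongside, so that comparison with other studies is kept.

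**Cost.** A few sentences and one extra display. No new data are needed: section 6.2 already has dates, route, dose and indication of concomitant therapies entered in the eCRF. The amendment details for V3.0 report no participants enrolled at that date.

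**Downside.** Rates may be slightly lower, by up to 6.7 points per affected participant with 15 evaluable. An early barred burst counts as non-response at every later month even if the participant then does well, which is a further reason to show both versions.

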### **9.3 Planned analyses**

The EOS analysis will be performed when all enrolled participants have completed the post-treatment follow-up period or discontinued the study.

### **9.4 Sample size**

A total of approximately 15 Chinese patients with SLE are planned to be enrolled.

## **10 REGULATORY, ETHICAL, AND STUDY OVERSIGHT CONSIDERATIONS**

### **10.1 Regulatory and ethical considerations**

The sponsor personnel and the investigators will ensure that the study is conducted in full compliance with ICH GCP guidelines, the principles of the Declaration of Helsinki, and with the laws and regulations of the country in which the study is conducted.

The investigator and/or sponsor/CRO will submit this protocol and any related documents provided to the participant (such as the ICF) to an IEC/IRB and to the health authority (as applicable). Approval from both the IEC/IRB and the health authority must be obtained

before starting the study and must be documented in a dated letter to the investigator and/or sponsor/CRO, clearly identifying the study, the documents reviewed, and the date of approval.

Modifications made to the protocol or the ICF after receipt of the approval must also be submitted as amendments by the investigator/delegate and/or sponsor/CRO to the IEC/IRB and to the health authority in accordance with local procedures and regulations.

## 10.2 Informed consent process

It is the responsibility of the investigator/delegate to obtain informed consent according to ICH GCP and Declaration of Helsinki guidelines and local regulations from each individual participating in this study. The investigator/delegate must explain to participants that they are completely free to refuse to enter the study, or to voluntarily withdraw from the study at any time for any reason without having to provide any justification. Special attention must be paid to the information needs of specific participant populations and of individual participants, as well as to the methods used to deliver the information. Adequate time must be given for the participant to consider his or her decision to participate in the study and it must be verified that the participant has understood the information (e.g., by asking the participant to explain what is going to happen).

If a revised version of the ICF is approved by health authorities (if applicable) and IRBs/IECs:

- Newly recruited participants must provide consent using the most current version of the ICF(s).
- Participants who are already participating in the study (e.g., already recruited) must re-consent using the most current version of the ICF(s), if necessary (e.g., additional study procedure, new safety information) and/or requested (e.g., as per IRB/IEC requirements).

The ICF will be provided, at a minimum, in the country's official local language(s) and as requested by health authorities (if applicable) and IRBs/IECs.

Site personnel authorized (according to local regulation) to participate in the consent process and/or to obtain consent from the participant will be listed on the Delegation of Authority form. A study physician or a healthcare professional with advanced practice, if allowed by local regulations must always be involved in the consent process.

The participant and authorized site personnel listed on the Delegation of Authority form must sign, personally date, and time the ICF before any study-related procedures (i.e., any procedures required by the protocol) begin. If the time is not included on the ICF due to

local regulations, the time of the ICF signature of the participant and investigator/delegate must be documented in the participant's medical charts.

A copy of the signed and dated ICF is given to the participant; the original is filed in the site documentation. The informed consent process must be fully documented in the participant's medical records. This must include, at a minimum, the study reference, the participant identification number, the date and, if applicable, time when the participant was first introduced to the study, the language in which the study was explained, the date, the time of consent, who participated in the consent discussion, who consented the participant, and any additional persons present during the consent process (e.g., participant's family member[s]), and the information that a copy of the signed ICF was given to the participant.

If a participant becomes pregnant during the study, she will be asked to sign a specific ICF to allow the collection of her health information during her pregnancy and from the baby(ies) following delivery. The father of the baby, if possible, will also be asked to sign the ICF.

If the site intends to recruit participants who are considered vulnerable (e.g., participant cannot read or write, does not speak or understand the ICF language), additional measures must be implemented to ensure the participant's rights are respected and the consent obtained is legally valid. The sponsor, the regulatory authorities (if applicable), and the IEC/IRB must be informed prior to the recruitment. The consent process (e.g., involvement of an impartial witness) must be fully described, submitted to, and approved by the IEC/IRB, according to procedures and before participants are recruited.

### **10.3 Data protection and privacy**

Participant data confidentiality and privacy are strictly held in trust by the investigators, their staff, and the sponsor or delegate.

The investigator/delegate must ensure that data confidentiality is maintained. On eCRFs or other documents (e.g., documents attached to SAE forms / Pregnancy forms) submitted to the sponsor and any vendors or CROs, participants must be identified only by number and never by their name or initials, date of birth, hospital numbers, or any other personal identifier. The investigator/delegate must keep a participant identification code list at the site. Documents identifying the participants (e.g., signed ICFs) must not be sent to the sponsor or any vendors or CROs, and must be kept in strict confidence by the investigator/delegate.

The participants must be informed that their personal study-related data will be used by the sponsor in accordance with local data protection laws.

The participants must be informed that their medical records may be inspected by the sponsor or sponsor's delegate, by appropriate IRB/IEC members, and by inspectors from regulatory authorities.

#### **10.4 Indemnification, compensation, and refund of expenses to participants and investigators**

The sponsor provides insurance in order to indemnify (with both legal and financial coverage) the investigator/site against claims arising from the study, except for claims that arise from malpractice and/or negligence.

The indemnification of the participants in the event of study-related injuries will comply with applicable regulations.

#### **10.5 Essential documents and retention of documents**

The investigator/delegate must maintain adequate records necessary for the reconstruction and evaluation of the study. Several attributes are considered to be of universal importance to source data and the records that hold those data. These include that the data and records are accurate, legible, contemporaneous, original (or a certified copy), attributable, complete, consistent, enduring, and available when needed.

These records will be classified into 2 different categories of document: ISF and participants' source documents.

These records must be kept by the investigator/site for as long as is necessary to comply with the sponsor's requirements (i.e., as specified in the clinical study agreement), ICH GCP and national and/or international regulations, whichever is the longest period. If the investigator/site cannot guarantee this archiving requirement at the site for any or all of the documents, special arrangements, respecting the data confidentiality, must be made between the investigator/site and the sponsor to store these documents off site, so that they can be retrieved in the event of a regulatory inspection. Study documents must not be destroyed without prior written approval from the sponsor. If the site needs to transfer the study records to another location and/or if the site facility can no longer store the study records, the investigator/site must immediately inform the sponsor.

##### **10.5.1 Investigator Site File**

Each site will maintain an ISF. It will contain all the essential documents that are required to be up-to-date and filed at the site as per ICH GCP section 8.

The ISF must be stored in a secure and access-restricted area during and after the study.

### **10.5.2 Source documents**

All source documents should be completed in a neat and legible manner to ensure accurate interpretation and traceability of the data. Data reported in the eCRF derived from source documents must be consistent with the source documents.

If the site is using electronic/computerized system(s) to store participants' medical records, it can be used for the purpose of the clinical study if it is validated (as per 21 CFR Part 11 or equivalent standard) and if the CRA has been provided personal access to participants' medical records in order to verify consistency between electronic source data and the eCRF during monitoring visits.

If the site is using electronic/computerized system(s) to store participant medical records but it cannot be confirmed that the system(s) is/are validated or if the CRA cannot be provided access to the system(s), the site is requested to print the complete set of source data needed for verification by the CRA. These printouts need to be produced via a controlled process in order to be considered as certified copies as defined in the ICH GCP (e.g., printout numbered, stapled together with a cover sheet, signed, and dated by the investigator / member of site staff to confirm that these certified copies are exact copies containing the same information as the original source data). The printouts will be considered as the official clinical study records. Once printed and certified, the document must not be edited/changed (e.g., manual notes added, clinical value changed) in order not to impact the validity of the certification. If the data need to be changed (e.g., correction of a mistake) the change(s) must be done in a traceable fashion and a new copy must be printed and certified.

In order to verify that the process the site uses to prepare certified copies is reliable, the CRA periodically requests that a site representative logs into the electronic/computerized system so the CRA could verify the entries in the system against the printouts. The CRA does not need to perform these activities for all participants but at least for some of them and for key data (e.g., eligibility criteria and primary endpoints) as per the sponsor/CRO instructions.

Paper source data will be collected by paper sheets:

- By trained and delegated site staff for clinical outcome assessments (SLEDAI-2K, SFI, PGA, BILAG, CLASI, and tender/swollen joint count) and supportive data from physical examination, weight, clinical symptoms, and medical evaluation of the participants.

